6.7. Immunogenicity

Blood samples to provide serum for detection of ADA (and neutralizing antibody) against ADG20 will be collected at timepoints specified in the Schedule of Assessments ([Table 12-1](#)). In addition to samples collected at scheduled visits, an additional blood sample should be collected from participants experiencing hypersensitivity reactions as described in Section [6.8.2](#). Additional instructions for sample collection, processing, storage, and shipping will be provided in the laboratory manual.

Immunogenicity may be assessed by a validated assay designed to detect ADAs in the presence of ADG20 at a laboratory approved by the sponsor or designee. Antibodies may be further characterized for their ability to neutralize the activity of ADG20. The sample analysis will follow a tiered approach of screening, confirmation, and titer determination.

6.8. Unscheduled Visits

6.8.1. COVID-19 Unscheduled Visits (Worsening, Relapse, or Recurrence)

Based on investigator's judgment, participants reporting worsening of signs or symptoms related to COVID-19 during the study may be referred to have an unscheduled study visit with site personnel or home health care provider. Participants will be referred to seek emergency medical care if emergency warning signs for COVID-19 should develop (trouble breathing, persistent pain or pressure in the chest, new confusion, inability to wake or stay awake, bluish lips or face). In the case of worsening COVID-19 not warranting emergency medical care, the site should perform an unscheduled visit, including saliva sample collection for RT-PCR testing and sequencing for SARS-CoV-2, collection of local and/or central safety laboratory samples per investigator discretion, vital signs, targeted review of changes in health, review of concomitant medications and adverse events, and medically attended visits assessment.

If at any time a participant reports a recurrence of COVID-19-like symptoms after having met the sustained recovery in the investigator's judgement or in the case of suspected re-infection, the site should perform an unscheduled visit, including saliva sample collection for RT-PCR testing and sequencing for SARS-CoV-2, collection of local and/or central safety laboratory samples per investigator discretion, vital signs, targeted review of changes in health, review of concomitant medications and adverse events, and medically attended visits assessment. This recurrence of symptoms will be treated as an AE (or SAE, if meeting criteria).

6.8.2. Hypersensitivity Reaction Assessment Unscheduled Visit

In the event that a participant reports a hypersensitivity reaction after Day 4 and outside of a regularly scheduled in-person visit, an unscheduled visit for evaluation of the reaction should be performed. This visit should include collection of samples for PK and ADA and collection of

local and/or central safety laboratory samples per investigator (or qualified designee) discretion using the unscheduled extra tube supply. Additionally, the following assessments should be performed: vital signs, a targeted review of changes in health, review of concomitant medications and adverse events, and medically attended visits collection.

Hypersensitivity reactions include but are not limited to anaphylaxis, anaphylactic shock, bronchospasm, hypotension, loss of consciousness, generalized skin rash, angioedema, bronchoconstriction, allergic bronchial asthma, allergic rhinitis, allergic conjunctivitis, drug allergy, immune thrombocytopenia, autoimmune hemolytic anemia, rash, urticaria, arthus reaction, etc.

6.8.3. Other Unscheduled Visits

An unscheduled visit may be necessary per investigator (or medically qualified designee) judgment for assessment of an AE or SAE or an abnormal lab or procedural findings. Repeat or unscheduled samples may be taken for safety reasons or for technical issues with the samples using the unscheduled extra supply kits.

6.9. Administrative Procedures

6.9.1. Visit Type Requirements

As outlined in the Schedule of Assessments, several visit types (in-clinic, home health, or telemedicine) will be utilized throughout the study.

In-person visits may be conducted in-clinic or as home health visits (where allowed by local regulations and as outlined in the Schedule of Assessments [[Table 12-1](#)]). Home health provider visits may also be combined with telemedicine contact with the site personnel, investigator, or medically qualified designee as needed. Home health visits will be at the location of the participant and may include a home health vendor to visit to a location other than the participants home such as a hospital or other location.

At all in-person visits (in-clinic or home health), site personnel or home health providers will follow institutional or local standards to prevent transmission of SARS-CoV-2. This may include procedures such as use of personal protective equipment for participants (and guardians/LARs), site staff, and home health providers and providing designated entry locations for study participants/guardians/LARs for visits.

Telemedicine visits may be conducted by various secure virtual means (eg, telephone, telehealth, videoconference, etc). At each visit, the identity of the participant must be confirmed based on local requirements and/or institutional procedures.

6.9.2. Use of eDiary

At the time of consent, the participants must confirm they will be willing to complete an eDiary (once daily through Day 29). The eDiary will be provided either through a device or an application downloaded to their mobile smart device (smartphone, tablet, etc) or a provided device (at site discretion/availability) at the time of enrollment.

- Before dosing on Day 1, the participant will be instructed how to access the eDiary on their personal mobile smart device or provided device.
- This study will preferably use the eDiary (via device or application) for the collection of COVID-19 symptoms; daily temperature, SpO₂, and heart rate; and ISRs.
- Participants or sites unwilling or unable to utilize an eDiary may be provided paper diaries for use (at site discretion/availability). Paper diaries may be used as back-up in the event eDiary is unavailable due to technological or other issues. Paper diaries should be collected from participants at all in-person visits.

6.9.3. Collection and Update of Contacts

In order to reduce lost to follow-up and ensure appropriate collection of medically attended visits for COVID-19, participants will be asked to provide primary and secondary contacts to the site staff. This data will not be entered into the eCRF.

The site will capture contact information for a primary and a secondary personal contact (eg, family member, friend, neighbor, etc). Additionally, sites will capture contact information for the participant's primary health care provider and the hospital/emergency care centers with closest proximity to the participant's home.

Primary and secondary personal contacts, health care provider contact and hospitals will be reviewed with the participant (or guardian/LAR) and updated at the visits outlined in the Schedule of Assessments ([Table 12-1](#)).

7. STATISTICAL CONSIDERATIONS

This section briefly describes the statistical and analytical methods to be used. An SAP will provide details of the statistical methods and definitions for the analysis of efficacy and safety data.

Enrollment in the study was suspended on 11-Jan-2022 after emergence and global spread of the Omicron variant in regions enrolling the trial, beginning in December 2021. Therefore, the primary analysis is focused on evaluating the efficacy of ADG20 300 mg IM in participants with a non-Omicron variant of SARS-CoV-2. With this analysis plan, the primary efficacy and short-term safety analyses are planned after a database soft lock. A final safety analysis will occur after all enrolled participants have been followed through 14 months/EOS, have discontinued, or if it is known that the Month 14 visit will not occur.

7.1. Sample Size Determination

The primary analysis is the comparison of the ADG20 arm versus the placebo arm with respect to the proportion of participants infected with a non-Omicron variant of SARS-CoV-2 with a COVID-19-related hospitalization or all-cause death through Day 29.

The original sample size was calculated based on assumptions obtained from a review of data from studies of other mAbs in participants at high risk for disease progression leading to hospitalization or death prior to widespread emergence of both the Delta and Omicron variants

(AstraZeneca 2022; Eli Lilly and Company 2022a; GlaxoSmithKline 2022; Regeneron 2022). The original sample size of 1084 participants was planned with 90% power, 2-sided alpha .05, and a 1:1 randomization ratio to detect a statistically significant risk reduction with a true efficacy of relative risk reduction 70% and a 5% event rate in the placebo arm.

At the time of enrollment suspension in January 2022, a total of 399 participants were randomized. Of them, approximately 320 participants will be included in the primary efficacy population of participants with a non-Omicron variant of SARS-CoV-2. Based on blinded monitoring of the primary endpoint outcomes, an approximate aggregate event rate of 9% was observed, indicating a higher placebo event rate than previously assumed and providing approximately 80% power to test the primary endpoint in the primary efficacy population given the same efficacy assumption.

7.2. Analysis Sets

The analysis sets that will be used for statistical analyses are defined in [Table 7-1](#). In the efficacy analyses, participants will be analyzed based on the treatment they are randomized to, irrespective of which treatment was actually received. In the safety analysis, participants will be analyzed based on the study drug received.

Table 7-1: Defined Analysis Sets and Descriptions

Defined Analysis Data Sets	Description
Full Analysis Set (FAS)	Includes all randomized participants regardless of whether the participant received study drug.
Modified Full Analysis Set with non-Omicron SARS-CoV-2 Variant (mFAS-non-Omicron)	Includes all randomized participants with COVID-19 due to WGS-confirmed or suspected non-Omicron SARS-CoV-2 variants, regardless of whether the participant received study drug. The mFAS-non-Omicron is the primary efficacy population.
Modified Full Analysis Set with Omicron SARS-CoV-2 Variant (mFAS-Omicron):	Includes all randomized participants with COVID-19 due to WGS-confirmed or suspected Omicron SARS-CoV-2 variant, regardless of whether the participant received study drug.
Modified Full Analysis Set-PCR (mFAS-PCR):	Includes all randomized participants with a positive baseline quantitative SARS-CoV-2 RT-PCR based on either an NP swab or saliva sample and who received study drug. Two sub-populations will be defined: 
• mFAS-NP: utilizes the baseline NP swab to determine a positive SARS-CoV-2 PCR• mFAS-S: utilizes the baseline saliva sample to determine a positive SARS-CoV-2 PCR.
mFAS-non-Omicron-PCR	Subset of the mFAS-non-Omicron with a positive baseline SARS-CoV-2 RT-PCR. The subpopulations mFAS-non-Omicron-NP and mFAS-non-Omicron-S based on sample type used to determine a positive SARS-CoV-2 PCR (as defined above) will also be analyzed.
mFAS-Omicron-PCR	Subset of the mFAS-Omicron with a positive baseline SARS-CoV-2 RT-PCR. The subpopulations mFAS-Omicron-NP and mFAS-Omicron-S based on sample type used to determine a positive SARS-CoV-2 PCR (as defined above) will also be analyzed.

Defined Analysis Data Sets	Description
Per-Protocol Set (PPS)	All mFAS-non-Omicron participants included who had no significant protocol deviations as defined in the SAP that affect the efficacy assessments and received treatment.
Safety Set	All participants who received any amount of study drug. All safety analyses will be conducted in this analysis set.
Immunogenicity Set	All participants who received any study drug, had a valid immunogenicity test result before the dose of study drug, and had at least 1 valid result after the dose of study drug.
PK Analysis Set	All participants in the Safety Set who had at least one measurable ADG20 concentration post-administration of study drug.

7.3. Subgroups of Interest

The primary and key secondary analyses in the mFAS-non-Omicron population will be repeated within subgroups of interest as defined in the SAP.

7.4. Statistical Analyses

Statistical analysis will be performed using SAS software Version 9.4 or later. Continuous variables will be summarized using the mean, standard deviation, median, first and the third quartiles, minimum value, and maximum value. Categorical variables will be summarized using frequency counts and percentages. Data will be listed.

The objectives and endpoints for all study phases are shown in [Table 2-1](#).

Unless otherwise specified, estimations involving the primary and secondary endpoints will follow a treatment policy strategy for the handling of intercurrent events, which uses and analyzes all data for the endpoints after the intercurrent event has occurred. When a hypothetical strategy is used, data may be censored in the case of a time to event endpoint or imputed in the case of continuous or binary endpoints.

Estimand attributes, intercurrent events of interest, and rationales for intercurrent event handling strategies for the primary and key secondary estimands will be fully described in the SAP. The main estimation for the primary efficacy and key secondary efficacy endpoints is described in [Section 7.6](#) and [Section 7.7](#). Definitions of censoring and details of imputation methodology will be provided in the SAP.

7.5. Multiplicity Adjustments

To control the overall type 1 error rate at .05 (2-sided), a hierarchical testing procedure will be used, such that testing for the key secondary analyses difference will proceed only if the treatment difference is statistically significant in the primary efficacy analysis. Analyses of the other secondary and exploratory endpoints will be conducted to support the findings of the primary and key secondary efficacy analyses without accounting for multiple comparisons. Nominal p-values and 95% CIs will be computed for these secondary and exploratory efficacy analyses.

7.6. Main Estimation Utilizing the Primary Efficacy Endpoint

The analysis of the primary estimand, incidence of COVID-19-related hospitalization or all-cause death through Day 29 in the ADG20 arm versus the placebo arm in the mFAS-non-Omicron analysis set will be analyzed using the methodology for determining a standardized estimator for a binary outcome as detailed in [Ge 2011](#), with adjustment for the following prognostic factors: age (continuous), sex (categorical), baseline qualitative serostatus (categorical), BMI (continuous), and baseline viral load (continuous). The standard error of the standardized estimator will be estimated using the delta method based on the algorithm presented in [Ge 2011](#). The risk difference (placebo minus ADG20) with CI (using the Miettinen-Nurminen method), standardized risk difference with CI, relative risk reduction with CI, and associated p-value for the standardized risk difference will be provided. A treatment policy strategy will be used to handle intercurrent events of interest. For example, treatment effect will be estimated regardless of baseline or emergence of coinfection with a non-SARS-CoV-2 pathogen, which is a potential intercurrent event of interest.

Supportive estimands for the primary efficacy objective will be fully described in the SAP.

7.7. Main Estimation Utilizing Key Secondary Efficacy Endpoints

The key secondary endpoints will be tested in the following order in the mFAS-non-Omicron analysis set:

1. Severe/critical COVID-19 or all-cause death through Day 29
2. COVID-19-related emergency room visit, COVID-19-related hospitalization, or all-cause death through Day 29.
3. Time to sustained resolution of COVID-19 symptoms through Day 29

Treatment differences in the proportion of participants with severe/critical COVID-19 or all-cause death through Day 29 will be presented with 95% CIs and tested using the analysis procedure outlined for the primary efficacy outcome.

Treatment differences in proportion of participants with COVID-19-related emergency room visits, COVID-19-related hospitalizations or all-cause death through Day 29 will be presented with 95% CIs and tested using the analysis procedure outlined for the primary outcome.

Time to sustained resolution in COVID-19 symptoms through Day 29 will be analyzed by KM methodology and stratified Cox Proportional Hazard model. Survival curves between ADG20 and placebo will be compared using a log-rank test stratified by age (categorical as 12-17, 18-65, and >65 years). A stratified Cox Proportional Hazard model will be used to estimate the hazard ratio where the model includes age (categorical as 12-17, 18-65, and >65 years) as stratification variable and sex (categorical), baseline serostatus (categorical), baseline BMI (continuous), and baseline viral load (continuous as \log_{10} copies/mL) as covariates. Comparison of the survival distributions will use the score test for the hazard ratio from the Cox model. Estimand attributes for the key secondary objective and supportive estimands will be fully described in the SAP.

7.8. Analyses of Other Secondary Efficacy Endpoints

Analyses of other secondary endpoints in the mFAS-non-Omicron analysis set will be conducted to support the findings of the primary and key secondary efficacy endpoints. Analysis approaches for the other secondary endpoints (ie, non-key) are summarized in [Table 7-2](#) .

Table 7-2: Analyses of Other Secondary Efficacy Endpoints

Endpoint	Statistical Analysis Methods
COVID-19-related medically attended visits or all-cause death through Day 29	Same as primary efficacy analysis (see Section 7.6).
Time to sustained recovery in COVID-19 symptoms through Day 29	Same as the analysis of time to sustained resolution of COVID-19 symptoms through Day 29.
All-cause death through Day 29, Day 60, and Day 90	KM methodology will be used to analyze all-cause deaths. The probability of all-cause deaths by each of these time points will be estimated, along with 95% CIs for differences in the probabilities. Survival curves between ADG20 and placebo will be compared using a log-rank test. A Cox Proportional Hazard model will be used to estimate the hazard ratio. The model includes age (continuous), sex (categorical), baseline serostatus (categorical: positive, negative), baseline BMI (continuous), and baseline viral load (continuous as \log_{10} copies/mL) as covariates. Comparison of the survival distributions will use the score test for the hazard ratio from the Cox model.
Change from baseline in SARS-CoV-2 viral load (\log_{10} copies/mL) to Day 7 (± 1) assessed by RT-qPCR from NP samples	Observed NP baseline and post-baseline values are used to calculate change from baseline. ANCOVA with treatment group and the prognostic factors (with observed NP baseline) as in the primary efficacy endpoint analyses as covariates will be performed. The LS mean for the point estimate in each group and 95% CIs will be presented. The difference in LS means between each ADG20 group and the placebo group and 95% CIs for the differences will be determined. The analysis will be performed on the mFAS-non-Omicron-NP, with available data at Day 7. In addition, two-sample t-test will be used to compare change from baseline viral load between treatment without covariate adjustment (unadjusted mean difference). If Day 7 value is missing, the earliest measurement closest to the Day 7 visit within 1 day (including scheduled and unscheduled visit) will be used.
Viral load >5 (\log_{10} copies/mL) on Day 7 (± 1) based on NP samples	Same as primary efficacy analysis (see Section 7.6). Analysis will be performed in mFAS-non-Omicron-NP with available data at Day 7. Analysis will be repeated using a second definition of high viral load (viral load $>4 \log_{10}$ copies/mL).

Endpoint	Statistical Analysis Methods
Duration of SARS-CoV-2 viral shedding from Day 1 through Day 29 assessed by RT-qPCR from saliva samples	KM methodology will be used to analyze duration of viral shedding from Day 1 through Day 29 by SARS-CoV-2 RNA defined as time from the first dose date to the first date the viral load is not detected, ie, below the limit of detection (LOD), and sustained through Day 29. KM curves will be compared between ADG20 and Placebo using a log-rank test stratified by age (categorical). A stratified Cox Proportional Hazard model will be used to estimate the hazard ratio where the model includes age (categorical as 12-17 years, 18-65 years and >65 years) as stratification variable and sex (categorical), baseline serostatus (categorical as positive; negative), baseline BMI (continuous) and baseline viral load (continuous as \log_{10} copies/mL) as covariates. Comparison of the survival distributions will use the score test for the hazard ratio from this Cox model. Analyses will be performed on the mFAS-non-Omicron-S. Deaths occurring prior to achieving cessation of viral shedding will be censored at Day 30.
Change from baseline in SARS-CoV-2 viral load (\log_{10} copies/mL) to Days 3, 5, 7, 11, 14, 21, and 29 assessed by RT-qPCR from saliva samples	Observed saliva baseline and post-baseline values are used to calculate change from baseline. Mixed model for repeated measures with treatment group and the prognostic factors (with observed saliva baseline) in the primary efficacy endpoint analysis as covariates will be performed. The LS mean for the point estimate in each group and 95% CIs will be presented. The difference in LS means between the ADG20 group and the placebo group and the 95% CIs for the differences will be determined. A plot of the LS means with 95% CIs by day assess by treatment group will be presented. The analysis will be performed on the mFAS-non-Omicron-S with available data at each timepoint. In addition, a two-sample t-test will be used to compare change from baseline viral load between treatment at each time point without covariate adjustment (unadjusted mean difference).
SARS-CoV-2 viral clearance (Days 5, 7, 11, 14, 21, and 29) assessed by RT-qPCR from saliva samples (and BLQ/not detected or not detected for NP sample for Day 7)	In the mFAS-non-Omicron-S, the cumulative proportion of participants with viral clearance will be presented for each post-baseline time point. In the mFAS-non-Omicron-NP, the proportion of participants with viral load BLQ/not detected at Day 7 will be presented. The ADG20 arm will be compared to placebo using the analysis procedure outlined for the primary efficacy outcome. In addition, these analyses will be presented for the subgroups of participants with observed baseline NP viral load >5 and $\leq 5 \log_{10}$ copies/mL. Deaths before achieving viral clearance will be considered to have no viral clearance.
SARS-CoV-2 viral load AUC (\log_{10} copies/mL) assessed by RT-qPCR from saliva samples through Day 29	An ANCOVA will be used to compare ADG20 and placebo where the prognostic factors in the primary efficacy endpoint analysis will be used as covariates. Participants in the mFAS-non-Omicron-S will be included in this analysis. The AUC from Day 1 through Day 29 will be calculated according to the linear trapezoidal rule using the measured SARS-CoV-2 viral load above the lower limit of quantification. No AUC values will be calculated when Day 1 and/or Day 29 values are missing, or if there are more than 3 values missing in the profile. In addition, two-sample t-test will be used to compare viral load AUC between treatment without covariate adjustment (unadjusted mean difference).

ANCOVA=Analysis of Covariance; BLQ=below limit of quantitation; CI=confidence interval; FAS=full analysis set; KM=Kaplan-Meier; LOD=limit of detection; mFAS=modified full analysis set; LS=least squares; RT-qPCR=quantitative reverse transcription polymerase chain reaction.

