Visit windowing rules: Assessments collected on the nominal visits per the protocol schedule will be included in by-visit summaries and analysis. If an assessment is missing from a nominal visit, available assessments from the unscheduled visits within the protocol-defined target-study-day range may be mapped to the corresponding nominal visit. The assessment occurring closest to the target study day will be used. If there are multiple assessments equally distant to the target study day, the earliest assessment will be used.

All diary data will be summarized based on the actual day.

Incomplete/missing data:

Imputation rules for missing dates of prior/concomitant medications, including COVID-19 vaccinations and prohibited medications, and procedures are provided in [Appendix C](#).

Imputation rules for missing AE are provided in [Appendix D](#).

Data that are continuous in nature but are reported in the form $< x$, $> x$, $\leq x$, or $\geq x$ (where x is considered as the limit of quantitation) will be set to limit of quantitation value with the following exceptions:

- For viral load data:
 - Viral load values reported as detected but BLQ of the PCR assay (<714 copies/mL) are imputed with half of LLOQ of the PCR assay (ie, 357 copies/mL)
 - Viral load values reported as not detected are imputed with 1 copy/mL (ie, $0 \log_{10}$ copies/mL)
 - All viral load analyses will use both observed and imputed viral load data. Listings present both observed and imputed viral load.
- For PK concentrations
 - Serum concentrations that are BLQ will be treated as zero for PK analyses, except for BLQ values observed between 2 quantifiable concentrations, which will be set to missing. If consecutive BLQ concentrations are followed by quantifiable concentrations in the terminal phase, those concentrations after BLQ concentrations will be treated as missing. Missing concentrations will be treated as missing in the PK parameter calculations.
- Efficacy endpoint data will be imputed as detailed in Section [5.5](#).
- Other incomplete/missing data will not be imputed, unless specified otherwise.

Treatment groups: The following treatment groups will be used for summary purposes:
ADG20, Placebo

All analyses and data summaries/displays for efficacy will be provided by treatment group using the appropriate analysis population unless otherwise specified.

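### The saliva viral-load MMRM names no baseline-by-visit term; read literally it uses one baseline slope for Days 3 to 29, which can cost precision at some visits and is free to correct

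*Protocol*

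**What the plan says.** Protocol 7.8 (Table 7-2) and SAP 5.5.4 (Table 4) give the model in the same words: "Mixed model for repeated measures with treatment group and the prognostic factors (with observed saliva baseline) in the primary efficacy endpoint analysis as covariates". The visits are "Days 3, 5, 7, 11, 14, 21, and 29 assessed by RT-qPCR from saliva samples". (The objectives tables of both documents list this endpoint only to Day 14; the check below follows the analysis tables.)

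Neither document writes visit, treatment-by-visit, baseline-by-visit, a covariance structure or a degrees-of-freedom method. The planned output, "A plot of the LS means with 95% CIs by day assess by treatment group will be presented", does require visit and treatment-by-visit. No planned output requires baseline-by-visit.

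On values below the assay limits, SAP 4.1 says "Viral load values reported as not detected are imputed with 1 copy/mL", that is 0 log10, and that detected values below quantification "are imputed with half of LLOQ of the PCR assay", that is 357 copies/mL. The same section applies these imputed values to all viral-load analyses.

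Alongside the model, "a two-sample t-test will be used to compare change from baseline viral load between treatment at each time point without covariate adjustment". On the population, "The analysis will be performed on the mFAS-non-Omicron-S with available data at each timepoint". The size of that set is not stated. It is a subset of the primary efficacy population, for which "approximately 320 participants will be included in the primary efficacy population".

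**The concern.** The outcome is change from baseline and the main covariate is baseline itself. For a participant whose virus is no longer detected, the SAP rule makes change exactly minus baseline. The slope of change on baseline therefore moves toward -1 over the visits as more participants clear. While virus is still quantifiable, nothing ties the slope to -1.

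One slope cannot fit both ends of that range. At visits where it is wrong, the adjusted treatment difference carries extra variance, and a chance baseline imbalance is removed by the wrong amount. Enrolment stopped at 399 randomised, so lost precision cannot be recovered by recruiting. SAP 5.5.5.2 also reuses the method in the smaller Omicron set.

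**Working it through.** **No figure to reproduce.** The documents give no SD, slope, effect size, clearance rate or power for this endpoint. Everything below except the imputation rules, the visits and the 320 is an assumption.

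**Step 1: what follows from the SAP alone.** Let x be baseline log10 viral load and y the later value. Not detected means y = 0, so change = 0 - x = -x and the slope is -1. Detected but below quantification means y = log10(357) = 2.55, a constant, so the slope within that group is also -1. This relies on the SAP 4.1 statement that imputed values are used.

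**Step 2: cost of a common slope (complete data).** Let b_t be the true slope at visit t, Ω the residual covariance with visit-specific slopes, ω_tt its diagonal, and σ² the baseline variance.

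- Common slope under unstructured covariance: c = (1'Ω⁻¹b)/(1'Ω⁻¹1).
- Variance of the treatment difference at visit t, relative to a visit-specific slope: 1 + (b_t - c)²σ²/ω_tt.
- The same ratio for an unadjusted comparison of change: 1 + b_t²σ²/ω_tt.

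**Step 3: assumed trajectories.** Log-linear decline with the SAP imputation, a detection limit of 2.3 log10, and the drug speeding decline by 20%. Columns 2 to 4 are inputs: baseline mean (SD) in log10; mean (between-person SD) decline in log10/day; measurement-noise SD.

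| Scenario | Baseline | Decline | Noise | b at Days 3 / 7 / 29 | c | Common slope, Days 3 / 5 / 7 | Unadjusted, Days 3 / 5 / 7 |
|---|---|---|---|---|---|---|---|
| Central | 6 (1.5) | 0.35 (0.12) | 0.7 | -0.13 / -0.04 / -0.92 | -0.65 | 1.57 / 1.49 / 1.39 | 1.03 / 1.01 / 1.00 |
| Low noise | 6 (1.5) | 0.35 (0.08) | 0.4 | -0.01 / +0.13 / -0.97 | -0.82 | 4.16 / 3.39 / 2.77 | 1.00 / 1.02 / 1.03 |
| High noise | 5.5 (1.3) | 0.35 (0.15) | 1.2 | -0.40 / -0.40 / -0.93 | -0.79 | 1.13 / 1.11 / 1.09 | 1.14 / 1.10 / 1.10 |
| Slow clearance | 6.5 (1.5) | 0.22 (0.10) | 0.8 | -0.20 / -0.15 / -0.65 | -0.27 | 1.01 / 1.01 / 1.02 | 1.09 / 1.06 / 1.03 |
| Fast clearance | 6 (1.8) | 0.60 (0.20) | 0.8 | -0.07 / -0.25 / -0.98 | -0.91 | 2.21 / 1.84 / 1.47 | 1.01 / 1.01 / 1.07 |
| Narrow baseline | 6 (1.0) | 0.35 (0.12) | 0.9 | -0.42 / -0.34 / -0.95 | -0.81 | 1.18 / 1.16 / 1.13 | 1.21 / 1.11 / 1.07 |

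Central case, Day 3, by hand: observed baseline SD 1.594 and residual SD 1.10 give 1 + (-0.13 + 0.645)² × 1.594²/1.10² = 1.56 (1.57 before rounding the inputs).

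**Step 4: dependence on the covariance structure.** If the common slope is the equal-weight average over visits, the central value is c = -0.38. The variance ratio is then 1.13 at Day 3 and 2.16 at Day 29, so the loss moves to late visits. Under unstructured covariance the central Day 29 ratio is 1.30.

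**Step 5: simulated trials.** 3000 trials of 320 participants (the upper bound for the saliva set), unstructured covariance, complete data.

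| Scenario | SE ratio, common / by-visit, Days 3 / 5 / 7 | Day 7 power, common vs by-visit |
|---|---|---|
| Central | 1.24 / 1.22 / 1.17 | 66% vs 80% |
| Low noise | 2.05 / 1.90 / 1.67 | 70% vs 99% |
| High noise | 1.06 / 1.06 / 1.04 | 45% vs 49% |
| Slow clearance | 1.01 / 1.01 / 1.00 | 46% vs 46% |

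Mean treatment differences were essentially the same under both models (central Day 7: -0.488 in each).

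**The case against.** **The text does not state a common slope.** A reader might infer that the plan chose one. It did not: the model line also omits visit, treatment-by-visit and the covariance structure, so it is an incomplete specification. That stands. But the by-day output forces the first two terms and nothing forces baseline-by-visit, so an analyst following the text would most naturally fit one slope.

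**The t-test covers the worst cases.** Where the early slope is near zero, the unadjusted comparison is close to optimal (central Days 3 to 7: 1.00 to 1.03). That also stands, and it means the early visits have a sound planned analysis. It does not rescue the adjusted result, which in the central case is less precise than the t-test at Day 3 (1.57/1.03 = 1.52). Nor does the t-test serve the late visits, where its central Day 29 ratio is 4.34.

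**The early visits need not be the ones that suffer.** A reader might infer that the slope is near zero early and that precision is lost where the drug acts. The documents give neither. Day 3 slopes ran from -0.01 to -0.42, and the pull of late visits on the common slope needs those visits to have low variance. If 20% were still detectable at Day 29 (assumed), the SD there would be at least 2.55 × √(0.2 × 0.8) = 1.02 log10. The slow-clearance case shows almost no early loss.

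**Visit-specific slopes may strain the model.** If nearly everyone has cleared by Day 29, little residual variance remains there and an unstructured matrix may not converge. Missing saliva samples were not simulated. This is fair, and it is why a fallback structure belongs in the fix.

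**Conclusion.** The point holds as a free improvement to an under-specified model. What is certain from the documents is that no baseline-by-visit term is listed and that the SAP imputation drives the slope toward -1 as virus clears. A common slope can therefore cost precision at some visits.

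The size and place of the loss cannot be determined from the documents. With unstructured covariance, assumed cases give extra variance at Days 3 to 7 of 1 to 2% (slow clearance), 9 to 18% (noisy assay or narrow baseline spread), 39 to 57% (central), and 47% to more than threefold extra (fast clearance or low noise). These are not properties of this trial.

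A reader might also infer a biased antiviral result. The check does not support that: with complete data, point estimates are essentially unchanged. A chance imbalance does leave an error in a single trial; for 0.2 log10 (assumed) at Day 3 in the central case it is (0.645 - 0.13) × 0.2 = 0.10 log10, but this averages out over randomisations. The endpoint is non-key secondary with nominal p-values (protocol 7.5). The t-tests, the Day 7 nasopharyngeal ANCOVA, and the primary and key secondary tests are untouched.

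**What to change.** In protocol Table 7-2 and SAP Table 4, before unblinding, specify the MMRM as treatment, visit, treatment-by-visit, saliva baseline viral load, saliva baseline-by-visit, age, sex, serostatus and BMI. State unstructured covariance, a named fallback structure if it does not converge, and the degrees-of-freedom method. Report the treatment difference at each visit from this model. The Omicron-set analysis in SAP 5.5.5.2 inherits the change by reference.

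The cost is a few sentences and six degrees of freedom (seven baseline slopes in place of one). It needs no new data. In none of the assumed scenarios was the visit-specific slope meaningfully less precise.
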